## 8.9 Clinical Laboratory Tests (Serum Chemistry, Hematology, and Urinalysis)

Clinical laboratory evaluations (clinical chemistry, hematology, and urinalysis) will be performed at Screening, Admission (Day -1), and at the time of discharge (Day 3) or as early termination assessments, as applicable.

Out-of-normal range flags will be recorded as follows: high (H) and low (L) for numerical results and did-not-match (\*) for categorical results. If a value fails the reference range, it will automatically be compared to a computer clinically significant (CS) range. If the value falls within the computer CS range, it will be noted as "N" for not clinically significant. If the value fails (i.e., fall outside of the CS range) the computer CS range, it will be flagged with a

Philip Morris Products S.A.  
THS Induction device and regular or menthol sticks, P1-PK-12  
[REDACTED] CA39924

---

"Y" which prompts the PI to determine how the out-of-range value should be followed using 4 Investigator flags: "N", not clinically significant, "R", requesting a recheck, "^", checking at the next scheduled visit, or "Y", clinically significant. To distinguish the PI flag from the computer CS range flags, the PI flags of "N" and "Y" will be presented as "-" and "+", respectively, in the data listing. Additionally, a derived flag based on a search of the PI comments for a comment of "CS" or "Clinically Significant" will be used. The derived flag will be populated with "+" if the positive clinically significant determination is found in the comments for cases when the PI flag is populated with a "^" or a "R".

Out-of-range values and corresponding recheck results will be listed. CTCAE laboratory grading (version 5.0) will be included as well. Other lab results within this panel and time point will also be listed for this subject. Results that are indicated as CS by the PI will be listed in the table.

For all numeric laboratory values, descriptive statistics will be presented for each laboratory test by time point (baseline and discharge). Change from baseline will be summarized in a similar manner. Baseline is defined as the result closest and prior to the first product administration, which may include unscheduled or recheck results. This will typically be the result collected on Admission (Day -1). Post product use unscheduled events or rechecks will not be included in summaries. Similarly, early termination results will not be included in summaries.

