## 8. SAFETY

All relevant case report form (CRF) data will be listed by subject and chronologically by assessment time point. This will include rechecks, unscheduled, and early termination assessments.

Applicable continuous variables will be summarized using n, mean, SD, minimum, median, and maximum.

The level of precision will be presented as follows: minimum/maximum in the same precision as in the database, mean/median in one more precision level than minimum/maximum, SD in one more precision level than mean/median, and n will be presented as an integer. Percentages will be presented as an integer.

Where individual data points are missing because of dropouts or other reasons, the data will be summarized based on reduced denominators.

Baseline will be the result closest and prior to the product use in the respective period unless otherwise stated. Summaries for post-baseline time points will not include rechecks, unscheduled, or early termination measurements.

Tables summarizing safety data by assessment time point will only include summaries for baseline and post-baseline time points.

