## 8.10 Vital Signs

Vital signs (systolic and diastolic blood pressure, pulse rate, and respiratory rate) will be measured at the Screening Visit, on Admission (Day -1), Preuse on Period 1, Period 2, and Period 3, and Discharge (Period 3) or as early termination assessments, as applicable. All parameters will be recorded in supine position after the subject has rested for at least 5 minutes. Subjects should have abstained from using any TNPs for at least 15 minutes prior to Vital signs assessment.

The Investigator will define vital sign ranges to determine normal or abnormal results. For those results outside of the normal range, the Investigator will determine appropriate follow up including reporting of any AEs.

Descriptive statistics will be reported for vital signs measurements (blood pressure, pulse, respiration, and temperature) by time point. Change from baseline will be summarized in a similar manner. Baseline is defined as the result closest and prior to the first product administration, which may include unscheduled or recheck results. This will typically be the result collected on prior to T0 on Day 1. Post product use unscheduled events or rechecks

Philip Morris Products S.A.  
THS Induction device and regular or menthol sticks, P1-PK-12  
[REDACTED] CA39924

---

will not be included in summaries. Similarly, early termination results will not be included in summaries.

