# = Lowest of the lower ranges and highest of the higher ranges are used. Refer to Appendix 16.1.10.1 for the breakdown.

\* = Above reference range; ^ = Below reference range

Program: /CAXXXX/sas\_prg/stsas/tab/programname2022Q1.sas DDMMYYYY HH:MM

Philip Morris Products S.A.

THS Induction device and regular or menthol sticks, P1-PK-12

CA39924

Page 1 of X

Table CLBS Clinical Laboratory Shift From Baseline - Serum Chemistry (Safety Population)

Laboratory Test (units)	Randomized Product Sequence	Time Point	Baseline L			Baseline N			Baseline H		
			Post Use			Post Use			Post Use		
			L	N	H	L	N	H	L	N	H
Testname (unit)	XXX	Discharge	X	XX	X	X	XX	X	X	XX	X
	XXX	Discharge	X	XX	X	X	XX	X	X	XX	X
	XXX	Discharge	X	XX	X	X	XX	X	X	XX	X
	XXX	Discharge	X	XX	X	X	XX	X	X	XX	X
	XXX	Discharge	X	XX	X	X	XX	X	X	XX	X
	XXX	Discharge	X	XX	X	X	XX	X	X	XX	X

Programmer Note: For urinalysis, the following footnote is used since the categories of N and O will be used instead of L, N, H:  
 N = Within reference range; O = Outside reference range

P1R: < >

P1M: < >

CIG: < >

Baseline is the last measurement collected prior to the first product administration.

N = Within reference range; L = Below reference range; H = Above reference range

Program: /CAXXXX/sas\_prg/stsas/tab/programname2022Q1.sas DDMMYYYY HH:MM

Philip Morris Products S.A.

THS Induction device and regular or menthol sticks, P1-PK-12

CA39924

Page 1 of X

Table CVS Vital Sign Summary and Change From Baseline (Safety Population)

Vital Sign (units)	Time Point	Statistic	Randomized Product Sequence					
			XXX (N = X)	XXX (N = X)	XXX (N = X)	XXX (N = X)	XXX (N = X)	XXX (N = X)
Testname (unit)	Baseline	n	X	X	X	X	X	X
		Mean	X.X	X.X	X.X	X.X	X.X	X.X
		SD	X.XX	X.XX	X.XX	X.XX	X.XX	X.XX
		Minimum	XX	XX	XX	XX	XX	XX
		Median	X.X	X.X	X.X	X.X	X.X	X.X
		Maximum	XX	XX	XX	XX	XX	XX
Day 2	Absolute	n	X	X	X	X	X	X
		Mean	X.X	X.X	X.X	X.X	X.X	X.X
		SD	X.XX	X.XX	X.XX	X.XX	X.XX	X.XX
		Minimum	XX	XX	XX	XX	XX	XX
		Median	X.X	X.X	X.X	X.X	X.X	X.X
		Maximum	XX	XX	XX	XX	XX	XX
Change	Change	n	X	X	X	X	X	X
		Mean	X.X	X.X	X.X	X.X	X.X	X.X
		SD	X.XX	X.XX	X.XX	X.XX	X.XX	X.XX
		Minimum	XX	XX	XX	XX	XX	XX
		Median	X.X	X.X	X.X	X.X	X.X	X.X
		Maximum	XX	XX	XX	XX	XX	XX

P1R: < >

P1M: < >

CIG: < >

Baseline is the last measurement collected prior to the first product administration.

Program: /CAXXXX/sas\_prg/stsas/tab/programname2022Q1.sas DDMMYYYY HH:MM

Philip Morris Products S.A.

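### A recheck can replace the safety baseline but not the post-use value; where out-of-range Day -1 results are rechecked, this tilts the laboratory shift tables toward normal-to-abnormal with no product effect

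*SAP*

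**What the plan says.** SAP 8.9 defines the laboratory baseline as follows: "Baseline is defined as the result closest and prior to the first product administration, which may include unscheduled or recheck results". It adds that this is usually the Day -1 result. For the other end of the comparison it says: "Post product use unscheduled events or rechecks will not be included in summaries". The vital-signs section has the same pair of rules (baseline is the last pre-use result, "which may include unscheduled or recheck results"), as do 8.11 (ECG) and 8.14 (spirometry). The introduction to SAP 8 repeats the exclusion for all safety data: "Summaries for post-baseline time points will not include rechecks, unscheduled, or early termination measurements". The footnotes of the CLBD, CLBS (shift), CVS, CEG and CSP shells carry the baseline half: "Baseline is the last measurement collected prior to the first product administration".

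On how laboratory rechecks arise, 8.9 says that a result outside the reference range but inside a computer clinically significant (CS) range is marked as not clinically significant. A result outside the CS range gets a flag "which prompts the PI to determine how the out-of-range value should be followed using 4 Investigator flags". Requesting a recheck is one of those four.

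Shift tables are listed for the three laboratory panels only (SAP 11.2, Tables 14.3.5.2, 14.3.5.4 and 14.3.5.6). Vital signs, ECG and spirometry have summary and change tables (14.3.5.7 to 14.3.5.9). In the shells all these tables are laid out by randomized sequence.

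**The concern.** A recheck prompted by an extreme value is a selective replacement, because the second measurement tends to lie closer to the subject's usual level. The SAP lets that replacement enter the summaries before use and bars it after use. The two ends of a change or shift are then selected differently, and abnormal values are thinned out at baseline only.

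Changes from baseline in these four domains are named secondary safety endpoints (Protocol 3.2, SAP 2). Discharge is the only post-use laboratory time point that is summarised, so each shift table rests on one comparison. The study has no concurrent unexposed group against which a spurious excess would cancel. A reader of the shift table could take it for an effect of exposure.

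**Working it through.** The documents give no recheck rate, CS limits, test-retest correlation or expected shift count, so there is no figure of the plan's own to reproduce. The check asks what the rule does when no product has any effect.

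**Inputs from the documents.** 30 subjects (Protocol 12.7.3). 13 hematology and 16 chemistry tests (Protocol Table 1, each differential cell type counted once). 29 × 30 = 870 values.

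**Assumptions.** Scheduled baseline B, baseline recheck R and scheduled post-use value P are standard normal with common correlation ρ = 0.5, 0.7 or 0.9. The reference range is ±1.96 SD, so 5% of first values are out of range. A recheck is done with probability p when B lies beyond a trigger of 1.96, 2.5 or 3 SD.

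**Formula.** The net excess is P(post-use abnormal) minus P(final baseline abnormal). The post-use value is always the scheduled one, so the first term is 0.05. Rechecking lowers the second term by p × Pr(B beyond trigger, R in range). Hence

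net excess = 870 × p × Pr(B beyond trigger, R in range).

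At ρ = 0.7 with a 1.96 SD trigger the joint probability is 3.34%, so the net excess is 870 × 0.0334 × p = 29.1 × p.

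**Shifts at ρ = 0.7 (normal-to-abnormal against abnormal-to-normal, of 870), with the net range over ρ = 0.9 to 0.5:**

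| Baselines rechecked | Shifts at ρ = 0.7 | Net, ρ = 0.9 to 0.5 |
|---|---|---|
| None (scheduled value at both ends) | 29 v 29 | 0 |
| All beyond 1.96 SD | 36 v 7 | 18 to 35 |
| Half of those | 32 v 18 | 9 to 18 |
| A quarter of those | 31 v 24 | 4 to 9 |
| All beyond 2.5 SD | 31 v 26 | 1 to 8 |
| All beyond 3 SD | 29.5 v 28.7 | 0 to 2 |

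The quarter row is 0.25 × 17.7 = 4.4 and 0.25 × 35.4 = 8.9. If only an upper limit matters, 2.5% of values are out of range and the all-rechecked net is halved, to 9 to 18.

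**Mean change.** With a symmetric two-sided range the replacements cancel and the mean bias is 0. With an upper limit only it is (1 − ρ) × φ(1.96) = (1 − ρ) × 0.0584 SD if all are rechecked: 0.029, 0.018 and 0.006 SD at ρ = 0.5, 0.7 and 0.9. The standard error of a mean change in 30 subjects is √(2(1 − ρ)/30) = 0.183, 0.141 and 0.082 SD. The bias is at most 0.029/0.183 = 16% of one standard error.

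**After a symmetric rule.** At ρ = 0.7 with every out-of-range value rechecked, scheduled values at both ends give 3.33% each way, and last values including rechecks at both ends give 1.07% against 1.09%.

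**The case against.** The strongest reply is that few rechecks can reach the baseline. Rechecks of Screening values are superseded by the Day -1 sample, so only a recheck in the roughly one day between that sample and first use counts. The SAP itself expects the baseline usually to be the Day -1 result. Its only described prompt is a value outside the CS range, and even then a recheck is optional. The one laboratory re-test in the protocol (7.5.1) is for a Screening sample unfit for analysis. This stands, and it is why the lower rows of the table may be the realistic ones. It does not remove the point. The SAP does not limit rechecks to the CS prompt, its laboratory, vital-signs and ECG listing shells provide for recheck values, and health is judged again at Day -1 for eligibility (inclusion criterion 5).

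It is also fair that the consequence is modest. Even the extreme case at ρ = 0.7 is 29 net shifts over 29 tests, about one per test in 30 subjects, or 1/6 = 0.17 per test per sequence column. The rule is the same in every sequence, no significance level is used, and out-of-range laboratory values are listed with their rechecks (Tables 14.3.4.1 to 14.3.4.3). The error points toward overstating harm. Listings let a reader trace a replaced baseline, but they do not correct the shift table.

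Finally, a symmetric rule does not guarantee balance. If every subject whose final baseline is out of range were excluded, scheduled values at both ends would still give 3.38% against 2.61% at ρ = 0.7. That part comes from selecting healthy subjects, not from the recheck rule.

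**Conclusion.** The asymmetry is in the text of all four sections and should be removed. Where out-of-range Day -1 laboratory values are rechecked, the shift tables tilt toward normal-to-abnormal with no product effect. Under the assumptions above, the net excess ranges from about 35 of 870 values (all rechecked, ρ = 0.5) to essentially none (3 SD trigger). The documents do not show where in that range this study would fall.

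A reader might infer that the change and shift tables in all four domains will show worsening whatever the products do. The documents do not support that. The tilt needs baseline rechecks, whose rate is not stated. Mean changes move by zero or by a small fraction of a standard error. Vital signs, ECG and spirometry have no shift table and no described recheck trigger, so for them the defect is an inconsistent definition only. Nor does the rule favour THS or CIG, since these tables are not by product.

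**What to change.** Apply one rule at both ends in SAP 8, 8.9, 8.10, 8.11 and 8.14 and in the footnotes of the CLBD, CLBS (shift), CVS, CEG and CSP shells:

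- Baseline is the last scheduled pre-use value: Day -1 for laboratory, ECG and spirometry; the pre-T0 value on Day 1 for vital signs; the repeated Day -1 visit for alternate subjects.
- The post-use value is the scheduled one.
- A recheck replaces either only when the scheduled result is technically invalid.
- Rechecks stay in the listings, and the number of values replaced at each end is reported.

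Using the last value including rechecks at both ends would also restore symmetry, but only if rechecks are done equally often before use and at Discharge. The scheduled-value rule does not depend on that.

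The cost is SAP wording and footnotes, with no change to data collection. A few baselines become the first, less normal value, and any tilt from selecting healthy subjects at Day -1 remains.

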5.2 Discontinuation of Subjects from the Study

Discontinued subjects will include both subjects who withdraw from the study (subject's decision) or subjects who are discontinued from the study by the decision of the Principal Investigator (PI).

Confidentiality Statement

Data and information contained in this document are considered to constitute trade secrets and confidential commercial information, and the legal protections provided to such trade secrets and confidential information are hereby claimed under the provisions of applicable law. No part of this document may be publicly disclosed without the written consent of Philip Morris Products S.A.

Subjects will be informed that they are free to withdraw from the study at any time. Subjects should be questioned for the reason of withdrawal from the study, although they are not obliged to disclose it.

If the subject withdraws from the study, this information will be fully documented by the PI or designee including:

- The early termination procedures for safety assessments will be performed as defined in Section 9.7, unless the subject refuses to perform the assessments.
- The samples collected up to the time of withdrawal that have been analyzed and data collected up to the time of withdrawal will be used in the analysis and report. If the subject refuses that non-analyzed samples and data will be used, he/she needs to document his/her disagreement in writing.

Subjects must be discontinued from the study for any of the following reasons:

- Withdrawal of informed consent
- Non-adherence to allocated product
- Subject becomes an employee of the investigational site, or any other parties involved in the study or their first-degree relatives (parent, sibling, and child)
- Any AE or condition (including clinically significant changes in a laboratory parameter) which at the discretion of the PI no longer justifies the subject's participation in this study
- Positive pregnancy test
- Discontinuation considered to be in the best interest of the subject or the other subjects, as judged by the PI
- Subject unwilling to use the product or to comply with abstinence as required
- An alternate subject that has completed the individual 28-day Screening period and has not been randomized

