7.5 Laboratory Assessments

7.5.1 Clinical Chemistry, Hematology, and Urine Analysis for Safety Panel

Hematology and clinical chemistry analysis will be assessed as per Schedule of Events. Subjects should have fasted for at least 6 hours prior to safety laboratory assessments, except at Discharge and Early termination where non-fasting samples can be used. Tests will be conducted at a local laboratory ([Appendix B](#)). If during the Screening visit a blood sample is not suitable for analysis (e.g., blood clotting) a re-test should be performed for the specific parameters which are not available. Safety urine analysis will be assessed at Screening, Baseline and at Discharge or at Early termination.

Parameters to be tested are listed in [Table 1](#).

Confidentiality Statement

Data and information contained in this document are considered to constitute trade secrets and confidential commercial information, and the legal protections provided to such trade secrets and confidential information are hereby claimed under the provisions of applicable law. No part of this document may be publicly disclosed without the written consent of Philip Morris Products S.A.

Table 1 Clinical Laboratory Parameters for Safety Panel

| Hematology | Clinical Chemistry | Urine analysis |
|--|---|---|
| 
 • Hematocrit • Hemoglobin • Mean corpuscular hemoglobin • Mean corpuscular hemoglobin concentration • Mean corpuscular volume • Platelet count • Red blood cell count • White blood cell count • Differential* WBC count: 
 - Neutrophils - Basophils - Eosinophils - Lymphocytes - Monocytes | 
 • Albumin • Total protein • Alkaline phosphatase • Alanine aminotransferase • Aspartate aminotransferase • Blood urea nitrogen • Creatinine • Gamma-glutamyl transferase • Glucose • Lactate dehydrogenase • Potassium • Sodium • Total bilirubin • Direct bilirubin • Total cholesterol • Triglycerides | 
 • pH • Bilirubin • Glucose • Nitrite • Red blood cell traces • Protein • Specific gravity |

*Differential WBC count both percentage and absolute

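### Early-termination results are left out of the change-from-baseline tables for laboratory tests, ECG and spirometry, where Discharge is the only other scheduled post-use value

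*SAP*

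**What the plan says.** The general rule in SAP 8 (Safety) reads: "Summaries for post-baseline time points will not include rechecks, unscheduled, or early termination measurements". The sections on laboratory tests (8.9), vital signs (8.10), ECG (8.11) and spirometry (8.14) each repeat it. In 8.9 the wording is "early termination results will not be included in summaries", and laboratory values are summarised "by time point (baseline and discharge") only. The table shells for ECG and spirometry also show only Baseline and Discharge, and the laboratory shift shell shows only Discharge.

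Vital signs differ. SAP 8.10 schedules them "Preuse on Period 1, Period 2, and Period 3, and Discharge (Period 3) or as early termination assessments, as applicable".

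The protocol treats early termination as the alternative to Discharge. Section 7.5.1 says: "Safety urine analysis will be assessed at Screening, Baseline and at Discharge or at Early termination". Sections 7.4.6 and 7.4.7 say the same for spirometry and ECG, and Table 8 in section 9.7 lists blood, urine, vital signs, ECG and spirometry among the early-termination procedures.

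The results remain in the report. Of the by-subject listings of case report form data, SAP 8 says: "This will include rechecks, unscheduled, and early termination assessments".

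**The concern.** Changes from baseline in laboratory values, ECG and spirometry are stated secondary safety endpoints (protocol 3.2). The SAP gives a planned end-of-participation assessment the same treatment as an unscheduled recheck. Where Discharge is the only other post-use assessment, this removes the subject's change from the table altogether.

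The reasons for stopping can be linked to the outcome. Protocol 5.2 requires discontinuation for "Any AE or condition (including clinically significant changes in a laboratory parameter") that, at the investigator's discretion, no longer justifies participation. A laboratory change could thus end a subject's participation and then be missing from the laboratory change and shift tables. A reader of those tables would be looking at subjects who reached Discharge.

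The SAP does not present this as a choice. Protocol 12.5.2 plans the change tables without any such exclusion. Protocol 5.2 says that data gathered up to withdrawal will be used in the analysis. SAP 9 declares the SAP aligned with the protocol and gives no reason for the exclusion.

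**Working it through.** The plan gives no figure to reproduce, because the point rests on which assessments exist and which tables they enter. For a subject who stops after at least one product use and before the Discharge assessments:

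| Measure | Scheduled values after first use | In change summary | In another Section 14 table | In listings |
|---|---|---|---|---|
| Laboratory | Discharge or early termination | None | Yes, if out of range or judged clinically significant | Yes |
| ECG | Discharge or early termination | None | No | Yes |
| Spirometry | Discharge or early termination | None | No | Yes |
| Vital signs | Pre-use Day 2, pre-use Day 3, Discharge or early termination | Pre-use Day 2 or Day 3, if reached | No | Yes |

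Sources: SAP 8 to 8.11, 8.14, the table and listing lists in SAP 11.2 and 11.3, and the shells in SAP 12.3.

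**Illustrative size.** Inputs from protocol 12.7.3 are 30 subjects and 6 sequences. Protocol 5.2 says that subjects who stop after randomization are not replaced, except on loss of a whole treatment group. Two inputs are assumed: balance across sequences, and the number of stops, since no dropout rate is given.

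- Subjects per sequence column: 30 / 6 = 5.
- Share of end-of-study values left out for d stops, d / 30: 1/30 = 3.3%, 2/30 = 6.7%, 3/30 = 10%. The tables then hold 29, 28 or 27 subjects.
- Share of one sequence column lost to one stop: 1/5 = 20%.
- If the omitted subject's change differs by D from the mean of the other four, the five-subject mean differs from the reported four-subject mean by D/5. The documents give no basis for a value of D.
- Chance that the rule affects at least one of 30 subjects at an assumed stopping rate r, 1 − (1 − r)^30: 45% at r = 2%, 79% at 5%, 96% at 10%.

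These figures show how often the rule could apply and how many values it would remove. They do not estimate any shift in a safety result.

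**The case against.** The strongest reply is that little is hidden. Every early-termination value is listed. The laboratory out-of-range table admits early-termination records that are out of range. When the investigator judges a laboratory value clinically significant, all time points for that subject and test are shown. Adverse events leading to discontinuation are tabulated (SAP 8.8), and the change tables print n at each time point beside a column N, so a gap is visible. All of this stands for laboratory values. It does not cover ECG or spirometry, whose only Section 14 tables are the change summaries.

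A reader might infer that early stoppers contribute no safety data, or that the summaries are biased towards no effect. The documents support neither. Beyond the safeguards above, pre-use vital signs on Day 2 or Day 3 may remain, and a subject who stops late on Day 3 may already have Discharge values. Many reasons for stopping in protocol 5.2 need not involve any physiological change, such as withdrawn consent, non-adherence to the product or sponsor termination. The omission is plausibly informative only for stops related to adverse events, and neither their number nor the direction of any effect is known.

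A further objection concerns the remedy. Moving early-termination values into the Discharge row would mix a subject who had used one or two products with subjects at the end of the full sequence, in tables split by sequence. That is a good reason to keep the Discharge row unmixed. It is not a reason to have no row that includes these subjects.

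Finally, the protocol's commitment covers data up to withdrawal, and early-termination assessments can be argued to come after it. Even so, protocol 9.7 collects them as safety assessments and section 12.5.2 does not exclude them. Leaving them out is a decision that the SAP should state and justify.

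**Conclusion.** The point holds for the change-from-baseline tables for laboratory tests, ECG and spirometry, and for the laboratory shift tables. A subject who stops after product use but before the Discharge assessments contributes no post-use value there, whatever the reason for stopping. For vital signs only the end-of-study value is lost. The gap matters most for ECG and spirometry, where early-termination values appear only in listings.

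The size is unknown. The 3% to 10% overall and 20% of a sequence column are illustrations that rest on 1 to 3 assumed stops and on balanced sequences. The stakes are modest: the safety analysis is descriptive, and exposure is three single uses over three days. The change is still worth making, because these are stated secondary endpoints, the data are already collected and the SAP declares no departure from the protocol.

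**What to change.** 1. Keep the Discharge row as planned. Add to the change-from-baseline tables and the laboratory shift tables a pre-specified row, *End of study (last post-use value, including early termination)*.
2. Footnote that row with the number of early-termination values and the products each of those subjects had used before stopping.
3. Amend the exclusion sentences in SAP 8, 8.9, 8.10, 8.11 and 8.14 so that they allow this row. Values taken before any product use stay out of it.
4. Reconcile SAP 9 with protocol 5.2 and 12.5.2. If the sponsor prefers to keep the exclusion, SAP 9 should declare and justify it.

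The cost is a few sentences of SAP text, one derivation rule and one extra row per table. The downside is that the new row mixes different times since use and different numbers of products used. The footnote discloses this, and the unmixed Discharge row remains beside it.
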